1.2.2. Justification for design

Randomised controlled trials are considered the "gold standard" for evidence-based medicine. As the intervention arm will involve withholding treatment the patient and research team are unable to be blinded from the treatment allocation. In order to minimise bias from an open label trial we will have a blinded end point committee to adjudicate outcomes.

A nested study of all CTPAs will be performed, comparing the SSPE diagnosis made by the acute reporting radiologists with specialist thoracic radiologists. This will allow us to determine safety in the pilot study (patients with larger than subsegmental clots are rapidly identified), appropriate powering and sample size (e.g. patients with breathing artefact may be recruited instead of true SSPE) and develop guidance for SSPE diagnosis in routine clinical practice. See section 3.3.1 for further details on this.

1.2.3. Choice of intervention

This trial is testing how a strategy of withholding anticoagulation in ISSPE (either symptomatic or incidental) for at least 3 months compares to standard care which is full anticoagulation for at least 3 months. We have not specified the choice of anticoagulation as there are contra-indications for directly acting oral anticoagulants (DOACs) such as renal impairment where warfarin would be an acceptable alternative. In some patients, low molecular weight heparin (LMWH) injected subcutaneously would also be appropriate. By not specifying the drug class of anticoagulation, we are testing the strategy of full anticoagulation against the strategy of no anticoagulation in the most generalisable and pragmatic way.

1.2.4. Process Evaluation

A process evaluation will be carried out to evaluate (1) the acceptability of the intervention (delivered during the internal pilot, see pilot objectives in the next section), (2) programme reach.

2. AIMS AND OBJECTIVES

2.1. Pilot Stage Objectives

The internal pilot will be conducted during the first 12 months of recruitment and has the following objectives:

- 1. To assess recruitment rates, the nature of exclusions and patients who decline.
- 2. To assess acceptability of the study to patients and clinicians and early identification of recruitment barriers.
- 3. To assess safety with respect to SSPE diagnosis (see 3.1.1 Nested CTPA Study).
- 4. To refine recruitment target based on misclassification rates.

Table 1: RAG rating for internal pilot

Table 1: 10 to facing for internal prior			
	% of patients declining no treatment	Patients recruited per site	
Red	≥70%	< 0.5 per month	
Amber	30-69%	0.5 – 1.5 per month	
Green	<30%	≥1.5 per month	

We have taken guidance from a Medical Research Council Hubs for Trials Methodology Research workshop into account when determining stop/go criteria and will report our pilot results according to their suggestions (27). Areas considered by the workshop as suitable progression criteria included recruitment rate, protocol adherence and outcome rate. As described in Table 1, the traffic light system of green (go), amber (amend) and red (stop) was deemed preferable to a simple stop/go approach when specifying progression criteria for internal pilot studies, and they suggested recruitment progression criteria should be based on rates per centre per unit time that can be extrapolated, rather than specifying an absolute number by a specific date.

Our first major progression criterion is the proportion of otherwise eligible patients excluded due to declining no treatment (green=<30%, amber= 30-69%, red= \geq 70%). Our second criterion is recruitment rate. If sites, overall, recruit 1.5 patients per month on average, and each site has a target of 30 patients each site will complete recruitment in 20 months; this represents green as recruitment would complete by 32 months, assuming a linear rate of site opening. If overall recruitment was 1 patient/site/month we would approach more sites to open, and if there were <0.5 patients/site/month this represents red (stop). We will collect safety data about VTE outcomes at 4 weeks after randomisation. The DMC will review safety data with respect to SSPE diagnosis (see 3.1.1 Nested CTPA Study) and recurrent VTE and recommend whether the trial should progress or not.

2.2. Main Trial Objectives

2.2.1. Clinical Aims and Objectives 2.2.1.1. Primary Objective

To determine if withholding anticoagulation is non-inferior to standard anticoagulation therapy in the treatment of ISSPE for preventing recurrent VTE, or death related VTE, or superior for clinically relevant bleeding over 3 months, compared with at least 3 months of full anticoagulation.

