Clinically relevant non- major bleeding (CRNMB)	Any sign or symptom of haemorrhage (e.g., more bleeding than would be expected for a clinical circumstance, including bleeding found by imaging alone) that does not fit the criteria for the ISTH definition of major bleeding but does meet at least one of the following criteria: i. requiring medical intervention by a healthcare professional ii. leading to hospitalisation or increased level of care

	iii. prompting a face to face (i.e., not just a telephone or electronic communication) evaluation ISTH major bleeding in non-surgical patients is defined as having a symptomatic presentation and: iv. Fatal bleeding, and/or v. Bleeding in a critical area or organ, such as intracranial, intraspinal, intraocular, retroperitoneal, intra-articular or pericardial, or intramuscular with compartment syndrome, and/or vi. Bleeding causing a fall in haemoglobin level of 20 g L ⁻¹ (1.24 mmol L ⁻¹) or more or leading to transfusion of two or more units of whole blood or red cells.	
Net clinical benefit	Composite of recurrent VTE and clinically relevant bleeding events.	
Active cancer	Cancer diagnosed within the past 6 months, cancer for which anticancer treatment was being given at the time of enrolment or during 6 months before randomisation, or recurrent locally advanced or metastatic cancer.	
Withholding	In relation to this trial withholding is defined as stopping the current treatment strategy of anticoagulation for at least 3 months.	

TRIAL SUMMARY

Title:

STOPping Anticoagulation for isolated or incidental subsegmental Pulmonary Embolism (STOP-APE)

Primary objective:

To determine if withholding anticoagulation is non-inferior to standard anticoagulation therapy in the treatment of isolated subsegmental pulmonary embolism (ISSPE) for preventing recurrent venous thromboembolism (VTE), or death related VTE, or superior for clinically relevant bleeding over 3 months, compared with at least 3 months of full anticoagulation.

Secondary objectives:

- Determine whether withholding anticoagulation for isolated subsegmental PE reduces harm (recurrent VTE, bleeding events) compared with at least 3 months of full anticoagulation at 6 and 12 months and impact on diagnoses of pulmonary hypertension at 12 months.
- Determine the reclassification rate of SSPE diagnoses made by acute reporting radiologists when reviewed by thoracic radiologists and formulate a set of rules to improve acute reporting radiologists' diagnoses of SSPE.

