- Determine whether any radiological parameters correlate with clinical presentations or outcomes.

Economic Aims and Objectives

- Healthcare resource use: hospitalisations, bed days, unscheduled primary and secondary care visits for recurrent VTE, clinically relevant bleeding or potentially related symptoms.
- Healthcare costs.
- Health-related quality of life (EQ-5D-5L at baseline, 12 and 24 weeks).
- Cost-utility at 24 weeks (cost per QALY) and cost-effectiveness at 52 weeks (cost per VTE avoided).

Mechanistic (behavioural) Aims and Objectives

- To determine whether not treating SSPE is acceptable to patients and clinicians.
- To determine the health seeking behaviours and health utilisation of a no anticoagulation treatment strategy for isolated SSPE.

Trial Design:

An investigator led, multicentre, prospective, randomised controlled, open-label, pragmatic clinical trial designed to test both the non-inferiority and superiority objectives. A 12-month internal pilot will assess feasibility and acceptability with safety of randomisation based on acute reporting radiologists' diagnoses assessed as part of a nested computed tomography pulmonary angiogram (CTPA) study.

Participant Population and Sample Size:

1466 consenting adult patients with ISSPE diagnosed on computed tomography pulmonary angiogram (CTPA) or computed tomography (CT) thorax with intravenous (IV) contrast.

Setting:

There will be approximately 50 trial sites from secondary care clinical settings of emergency departments, ambulatory care and acute medical units within NHS hospitals in the UK.

Eligibility Criteria:

Inclusion

- Age ≥18 years
- SSPE diagnosed by the radiologist at the trial site by CTPA or CT thorax with IV contrast
- No evidence of proximal deep vein thrombosis on doppler ultrasonography or CT / MR venography
- Heart rate (<110bpm)
- Systolic blood pressure (≥100 mmHg)
- Oxygen saturation (≥90%)
- Written signed informed consent to the trial

Exclusion

- Indication for hospital admission
- >7 days empirical anticoagulation treatment immediately prior to randomisation
- <28 days since first symptoms of proven or clinically suspected COVID-19
- Known stage 5 chronic kidney disease
- Patients with active cancer defined as cancer diagnosed within the past 6 months, cancer for which anticancer treatment was being given at the time of enrolment or during 6 months before randomisation, or recurrent locally advanced or metastatic cancer

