3. TRIAL DESIGN AND SETTING

3.1.Trial Design

STOP-APE is an investigator led, multicentre, prospective, randomised controlled, open-label, pragmatic clinical trial with central, blinded, independent adjudication committee (CIAC) endpoint assessment over 3 months for efficacy of withholding anticoagulation for ISSPE. The trial is designed to test the superiority for bleeding events and non-inferiority for recurrent VTE.

Participants will be randomised to either the control arm: full dose anticoagulant treatment as standard care, or the intervention arm: withholding anticoagulation. The choice of anticoagulant will be determined by the responsible treating clinician as part of the standard of care. Pre-randomisation empirical anticoagulation treatment will be allowed for up to 7 days immediately prior to randomisation.

The joint (multiple) primary outcomes of recurrent VTE and clinically relevant bleeding will be established from the trial site clinical notes and electronic health records, patient trial follow-ups and centralised data from hospital episode statistics (HES). The local research team will conduct a safety telephone follow up at 4 weeks, with a permitted window of 1 week either side. Trial follow-ups at 12 and 24 weeks will be performed by the local research team via telephone to complete case report forms and questionnaires. A window of \pm 2 weeks will be permitted for follow-ups.

A 12-month internal pilot will assess feasibility and acceptability with safety of randomisation based on acute reporting radiologists' diagnoses, assessed as part of a nested CTPA study. Note: The nested CTPA study will not stop after the 12-month internal pilot phase and so will be conducted for the full duration of the trial.

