13. STATISTICAL CONSIDERATIONS

13.1.Sample Size

The trial is powered on the superiority for bleeding events and non-inferiority for recurrent VTE.

Superiority for bleeding events:

With 90% power and two-sided alpha=0.05, to detect a decrease in major bleeding or CRNMB from 7% (based on a meta-analysis of DOAC RCTs)² in the anticoagulation group to 3% in the no anticoagulation group using a two-sample proportions test, 1244 patients (622 per group) are required.

Non-inferiority for recurrent VTE:

We also aim to detect whether no anticoagulation is non-inferior to treatment with anticoagulation regarding VTE recurrence. With 90% power, and a one sided alpha=0.025, a VTE recurrence rate of 2% with anticoagulation (also based on the DOAC RCT meta-analysis)² and a non-inferiority margin of 2.5%, 1,320 patients would be needed. Taking the largest of the two sample sizes computed (i.e. sample size for non-inferiority), allowing for 10% attrition, a total of 1466 patients (733 per arm) would be needed. Sample size calculations were performed using Stata 13.

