13.2. Analysis of Outcome Measures

A separate Statistical Analysis Plan will be produced and will provide a more comprehensive description of the planned statistical analyses. A brief outline of these analyses is given below.

The primary comparison groups will be composed of those treated without anticoagulation versus those treated with anticoagulation. All analyses will be based on the intention to treat principle as well as the per-protocol, with per-protocol set being patients with confirmed SSPE based on CTPA review.

For all outcome measures, appropriate summary statistics will be presented by group (e.g. proportions/percentages, mean/standard deviation or median/interquartile range). Intervention effects will be adjusted for the minimisation variables listed in section 6.2 and baseline scores where possible. 95% confidence intervals (CI) and p-values will be presented for all outcomes. No adjustment for multiple comparisons will be made.

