13.2.2. Secondary Outcome Measures

The secondary outcomes are a combination of binary data, continuous data and count data.

Binary outcomes:

The secondary outcomes that are binary (e.g. VTE related death) will be analysed using the same methods described for the co-primary outcomes (see Section 13.2.1).

Continuous outcomes:

For those secondary outcomes that are continuous (e.g. EQ-5D-5L), linear regression methods will be used for analysis. Results will be presented as adjusted mean difference. If data is found to be not normally distributed, then transformation of the data to get it into a normally distributed form (e.g. log-transformation) will be conducted prior to any analysis.

Count data outcomes:

For those secondary outcomes that are count data types (e.g. Hospitalisations, Unscheduled visits), Poisson regression model will be used for analysis. Time will be used as an offset in the model. Results will be presented as an adjusted incidence rate ratio.

Reclassification rates from thoracic radiologist review:

Reclassification rates for all recruited patients will be calculated with 95% binomial exact confidence intervals for (a) no SSPE and (b) PE requiring anticoagulation as the risks arising from misclassification are different in these patients' populations with implications for implementation as NHS practice does not currently include radiological review. These rates will be analysed without any adjustment. These reclassification rates by trial arm will be included in the table of baseline characteristics. Variation between centres will be described anonymously as understanding centre contribution to reclassification rates may be relevant to intervention implementation. Radiological review of the SSPE diagnosis by the acute reporting radiologist is required as a safety check to ensure randomised patients receive appropriate treatment, that is, anticoagulation of patients with no SSPE randomised to anticoagulation can be halted and anticoagulation of patients with PE which requires it can be initiated.

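### The primary objective joins VTE non-inferiority and bleeding superiority with 'or', while the design and sample size sections join them with 'and'; the rule for success needs to be fixed as both.

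*Protocol*

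**What the plan says.** Section 2.2.1.1 of the protocol sets out to determine whether withholding is non-inferior "for preventing recurrent VTE, or death related VTE, or superior for clinically relevant bleeding over 3 months". The first 'or' in that phrase lies inside the VTE composite. The second separates the two primary tests. The Trial Summary repeats it: "or superior for clinically relevant bleeding over 3 months, compared with at least 3 months of full anticoagulation".

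Other parts of the protocol join the tests differently:
- Trial Summary, Trial Design: "designed to test both the non-inferiority and superiority objectives".
- Section 3.1: "The trial is designed to test the superiority for bleeding events and non-inferiority for recurrent VTE".
- Section 13.1: "The trial is powered on the superiority for bleeding events and non-inferiority for recurrent VTE".
- Section 13.2.2 refers to "the same methods described for the co-primary outcomes".

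Sections 3.1, 8.2.1 and 13.2.1 call the outcomes joint and multiple. Section 8.2.1 labels recurrent VTE (with VTE-related death) the primary safety outcome and clinically relevant bleeding the primary efficacy outcome. Section 13.1 gives 90% power for each test separately and takes the larger sample size. Section 13.2 adds: "No adjustment for multiple comparisons will be made". No section says whether one or both tests must succeed.

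**The concern.** A reader cannot derive a single rule for success from these statements, and the two candidate rules have different consequences.

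If either test suffices, there are two unadjusted routes to a positive primary result. One of them is a fall in bleeding, which the protocol itself expects when anticoagulation is withheld. The objective could then be reported as met although non-inferiority on the primary safety outcome had not been shown.

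If both tests must succeed, no alpha adjustment is needed, because a false overall claim requires rejecting whichever null is true, and each is tested at its full level. The relevant power is then that of both tests together, which 13.1 does not give.

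The choice matters beyond the analysis, since 3.3.2 anticipates that achieving the primary outcome would change clinical guidelines.

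**Working it through.** **Inputs (protocol 13.1).** Bleeding: 7% against 3%, two-sided alpha 0.05, 90% power. VTE: 2% with anticoagulation, margin 2.5 percentage points, one-sided alpha 0.025, 90% power. Attrition: 10%. Allocation is 1:1 (6.4.1). The VTE rate in the withholding arm is not stated. I assume 2%, which reproduces the protocol's figure.

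**Reproducing the stated sizes** (normal quantiles 1.960 and 1.2816)
- Bleeding, pooled variance under the null: n = [1.960 × √(2 × 0.05 × 0.95) + 1.2816 × √(0.07 × 0.93 + 0.03 × 0.97)]² / 0.04² = 621.8, so 622 per arm and 1244 in total. This agrees.
- VTE, unpooled variance: n = (1.960 + 1.2816)² × (2 × 0.02 × 0.98) / 0.025² = 659.02, so 660 per arm and 1320 in total. This agrees.
- Attrition: 1320 / 0.9 = 1466.7, against 1466 stated. The difference is rounding.

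**Power of each test at 660 evaluable per arm**
- Bleeding: null standard error √(0.095/660) = 0.0120 and alternative standard error √(0.0942/660) = 0.01195. Φ[(0.04 − 1.960 × 0.0120)/0.01195] = 0.9162.
- VTE: standard error √(0.0392/660) = 0.00771. Φ(0.025/0.00771 − 1.960) = 0.9004.

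**If either test suffices**
- Put true VTE at 4.5% against 2%, exactly at the margin. Non-inferiority is then shown with probability Φ(0 − 1.960) = 0.025.
- The objective is still met through bleeding alone with the following probabilities:

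| True bleeding, control vs withheld | Probability of bleeding superiority |
|---|---|
| 7% vs 3% | 0.916 |
| 7% vs 4% | 0.67 |
| 7% vs 5% | 0.33 |

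- If both nulls hold (no bleeding reduction, VTE at the margin) and the tests are independent, the chance of at least one false favourable claim is 1 − 0.975² = 0.049 one-sided.

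**If both tests must succeed**
- Independent tests, 660 per arm: 0.9162 × 0.9004 = 0.825. A binomial simulation under independence gave 0.830.
- Any dependence, 660 per arm: lower bound 0.9162 + 0.9004 − 1 = 0.817; upper bound is the smaller of the two powers, 0.900.
- All 733 per arm evaluable, independent: 0.9406 × 0.9277 = 0.873.

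**The case against.** The strongest reply is that 2.2.1.1 is an objective and not a decision rule: it lists two questions and sets no criterion for success. The words 'both', 'and' and 'co-primary' elsewhere suggest that the investigators meant both. Section 13.2 also defers detail to a statistical analysis plan that is not shown, and the rule for combining the two results may be there. Much of this stands. A reader might infer that the protocol has adopted an either/or rule, but the text does not settle that. What remains is the conflict itself. A later plan could resolve it only by departing from one of the protocol's own statements.

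A reader might also infer that the trial has less power than stated. The document does not support that. Section 13.1 gives 90% for each test, both figures reproduce, and no joint figure is claimed. The 82.5% is also conditional. Section 7.4 starts anticoagulation after a recurrent VTE in the intervention group, so independence is not assured, and 3.3.1 allows the recruitment target to rise.

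A third tempting reading is that the objective would almost certainly be met whatever happens to VTE. That holds only at the planning effect for bleeding, as the table shows.

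Finally, excess VTE would not be hidden. It is a named primary outcome with a reported risk ratio and risk difference (13.2.1), the DMC reviews it (2.1), and net clinical benefit is a secondary outcome (8.2.2). That limits the harm but does not define success.

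**Conclusion.** The concern holds as an internal contradiction about what meets the primary objective. The 'or' appears in both statements of the objective and conflicts with the Trial Design entry of the Trial Summary and with 3.1, 13.1 and 13.2.2. The absence of multiplicity adjustment in 13.2 is right if both tests are required and unsuitable if either is enough.

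The literal reading would allow a positive result on bleeding alone about 92% of the time at the planning effect, with VTE at the margin. The 4.9% error figure is narrower: it needs no true bleeding benefit, VTE exactly at the margin, and independent tests. Each separate claim stays at one-sided 2.5%.

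The joint power of about 82% is a useful addition to the plan, not a correction of a stated number. It rests on independence, 660 evaluable per arm and 2% VTE in both arms.

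**What to change.** 1. In the Trial Summary and 2.2.1.1, replace 'or superior' with 'and superior'.
2. In 13.2, state that the primary objective is met only if VTE non-inferiority and bleeding superiority are both shown, each at its full level with no alpha adjustment, and that bleeding superiority alone does not meet it.
3. In 13.1, keep 90% as the power of each test. Add that power for both together is about 82%, assuming independence, 660 evaluable per arm and 2% VTE in both arms. Give the range of 81.7% to 90.0% under any dependence, and about 87% under independence if all 733 per arm are evaluable.

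A fixed sequence testing VTE first would also remove the ambiguity, but requiring both is closer to the wording of the design sections. The change should be made before comparative outcome data are seen.

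The cost is a few sentences and a less favourable joint power figure. No extra patients are needed if that figure is accepted. Joint power of 90% under independence would instead need about 787 evaluable per arm, that is 1574 / 0.9 = 1749 randomised.

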2.2.1.2. Secondary Objectives

- Determine whether withholding anticoagulation for isolated subsegmental PE reduces harm (recurrent VTE, bleeding events) compared with at least 3 months of full anticoagulation at 6 and 12 months and impact on diagnoses of pulmonary hypertension at 12 months.
- Determine the reclassification rate of SSPE diagnoses made by acute reporting radiologists when reviewed by thoracic radiologists and formulate a set of rules to improve acute reporting radiologists' diagnoses of SSPE.
- Determine whether any radiological parameters correlate with clinical presentations or outcomes.

